1.0 DOCUMENT HISTORY

Version	Date	Changes made since previous version
1.00	4 Nov 2019	Original
1.01	12 Nov 2019	Section 9.1 – Corrected typographical errors.

2.0 LIST OF ABBREVIATIONS

Abbreviation	Definition
AE	adverse event
ADR	adverse drug reaction
CFR	Code of Federal Regulations
CRA	clinical research associate
CRF	case report form
C-SSRS	Columbia – Suicide Severity Rating Scale
EDS	Excessive daytime sleepiness
ESS	Epworth Sleepiness Scale
FDA	Food and Drug Administration
GCP	Good Clinical Practice
Ham-D	Hamilton Depression Rating Scale
ICF	informed consent form
ICH	International Conference on Harmonisation
ICSD-3	International Classification of Sleep Disorders, Third Edition
IEC	Independent Ethics Committee
IIT	Intention-to-treat
MedDRA	Medical Dictionary for Regulatory Activities
MSLT	Multiple sleep latency test
██████	██
NSAQ	Narcolepsy Symptom Assessment Questionnaire
PGI-S	Patient Global Impression of Severity
PSG	polysomnography
SAE	serious adverse event
SAP	Statistical Analysis Plan
SD	standard deviation
SOC	system organ class
SSRIs	selective serotonin reuptake inhibitors
TCAs	tricyclic antidepressants
TEAE	treatment-emergent adverse event
US	United States
WHO	World Health Organization

3.0 INTRODUCTION

This statistical analysis plan (SAP) is based on [Protocol AXS-12-201, Amendment 2](#), dated 25 Apr 2019.

The purpose of this document is to provide details on study populations and on how the variables will be derived, how missing data will be handled, as well as details on statistical methodologies to be used to analyze the safety and efficacy data from the study.

The document may evolve over time, for example, to reflect the requirements of protocol amendments or regulatory requests. However, the final SAP must be finalized, approved by the Sponsor, and placed on file before the database is locked and treatment codes are unblinded. The approved plan will be used to carry out all analyses for the clinical study report. Deviations, if any, from the approved plan will be noted in the clinical study report.

4.0 STUDY DESCRIPTION

4.1 STUDY OBJECTIVES

The primary objective of the study is to assess the effect of AXS-12 as compared to placebo on the number of cataplexy attacks as recorded in a Sleep and Symptom Daily Diary.

The secondary objectives of the study are to assess the the effect of AXS-12 as compared to placebo on the following measures:

- Epworth Sleepiness Scale (ESS)
- Ability to Concentrate in the Sleep and Symptom Daily Diary
- Number of inadvertent naps or sleep attacks in the Sleep and Symptom Daily Diary
- Individual items of the Narcolepsy Symptom Assessment Questionnaire (NSAQ)
- [REDACTED]
- Hamilton Rating Scale for Depression (HAM-D)

4.2 STUDY TREATMENTS

In this crossover study all subjects will be randomized in a 1 : 1 ratio to Sequence 1 or Sequence 2. Subjects in Sequence 1 will receive AXS-12 in Period 1 and placebo in Period 2. Subjects in Sequence 2 will receive placebo in Period 1 and AXS-12 in Period 2.

4.3 STUDY DESIGN

This study is a three-week, crossover, multi-center, randomized, double-blind, placebo-controlled proof-of-concept Phase 2 trial to assess the safety and efficacy of AXS-12 in narcoleptic subjects with cataplexy and excessive daytime sleepiness (EDS). Eligible subjects must have a diagnosis of narcolepsy per the International Classification of Sleep Disorders, Third Edition (ICSD-3) criteria, and exhibit symptoms of both cataplexy and EDS. Subjects meeting the entry criteria will be randomized in a 1:1 ratio either to placebo for three weeks followed by AXS-12 (up to 10 mg daily) for three weeks, or to AXS-12 (up to 10 mg daily) for three weeks followed by placebo for three weeks. Study medication will be down-titrated during the third week of each three-week treatment period.

The primary endpoint will be the change in the number of cataplexy attacks as recorded in a Sleep and

Symptom Daily Diary. Secondary outcome measures will include the Epworth Sleepiness Scale (ESS), Hamilton Rating Scale for Depression (HAM-D), the Narcolepsy Symptom Assessment Questionnaire (NSAQ), and the Ability to Concentrate item of the NSAQ as assessed in the Sleep and Symptom Daily Diary.

Screening Period

All subjects will enter an up to three-week screening period (Screening, Visit 1) to determine eligibility. The screening period may last across multiple days / visits. During the screening period, an all-night polysomnography (PSG) followed by multiple sleep latency test (MSLT) may be required to confirm eligibility. Longer screening periods may be allowed to ensure washout of prior cataplexy medications.

Treatment Periods

Subjects meeting the entry criteria will be randomized in a 1:1 ratio either to placebo for three weeks followed by AXS-12 (up to 10 mg daily) for three weeks, or to AXS-12 (up to 10 mg daily) for three weeks followed by placebo for three weeks. Study medication will be down-titrated during the third week of each three-week treatment period.

Doses will be titrated to a target dose of 10 mg [redacted] during each treatment period [redacted]

- Week 1 (Day 1 – Day 7): [redacted] over-encapsulated reboxetine tablet in the morning and [redacted] over-encapsulated reboxetine tablet in the afternoon [redacted]
- Week 2 (Day 8 – Day 14): If tolerated, increase dose to [redacted] over-encapsulated reboxetine tablets in the morning and [redacted] over-encapsulated reboxetine tablet in the afternoon [redacted]

[redacted] Subjects will be monitored for safety and tolerability at each titration step.

[figure not shown]
All study medication will be of similar appearance in order to maintain the integrity of the blind.

All doses will be taken orally on an empty stomach (at least 2 hours pre- or post-prandial) with water.

Assessments and Visits

On Day 1 (Visit 2) eligible subjects will undergo baseline assessments and administration of the first dose of study drug in clinic. Subsequent study visits will occur on Days 15, 22, 36, and 42 (Visits 3-6). Study procedures and assessments will be performed during study visits as outlined in the Schedule of Assessments.

Study Design Schematic

4.4 RANDOMIZATION AND BLINDING

Subjects meeting the entry criteria will be randomized in a 1:1 ratio either to placebo for three weeks followed by AXS-12 (up to 10 mg daily) for three weeks, or to AXS-12 (up to 10 mg daily) for three weeks followed by placebo for three weeks. Study [REDACTED]

Detailed blinding and unblinding procedures can be found in the protocol.

5.0 ANALYSIS POPULATIONS

5.1 RANDOMIZED POPULATION

The randomized population will consist of all subjects who complete the Screening Phase and are randomized to a treatment sequence.

5.2 SAFETY POPULATION

The safety population will include all subjects who have received study medication. All safety analyses will use the safety population.

5.3 MODIFIED INTENT-TO-TREAT POPULATION

The Modified Intent-to-Treat (mITT) population will be the primary efficacy analysis population and will consist of all subjects who are randomized, subsequently take at least 1 dose of the study drug, and have at least 1 post-dose efficacy assessment.

5.4 PER PROTOCOL POPULATION

The Per Protocol population will include all subjects in the mITT population with no major protocol violations. Major protocol violation criteria will be established prior to the database lock. Protocol deviations will be presented in the clinical study report. Efficacy analyses may also be performed based on the per protocol population.

6.0 GENERAL CONVENTIONS

Unless otherwise stated, all analyses will be performed [REDACTED] and all hypothesis tests will be conducted at a two-sided significance level of 0.05. P-values will be presented with 3 decimals and p-values that are less than 0.001 will be presented as <0.001.

Continuous data will be summarized using descriptive statistics: number of observations (n), mean, standard deviation (SD), median, minimum, and maximum. Frequencies and percentages will be used to summarize categorical (discrete) data. Presentations of categorical data will generally suppress percentages for items where the count is zero in order to draw attention to the nonzero counts. In general, mean, standard deviation, median, minimum, maximum, and percentages will be presented with one decimal.

Unless otherwise stated, confidence intervals, when presented, will be constructed at the two-sided 95% level. For binomial variables, the 95% confidence intervals will be constructed using the normal approximation without continuity correction.

Data listings will present all data collected on CRFs by study drug, center, and subject number.

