10.0 SUMMARIES OF MEASURES OF SAFETY

Safety analyses will be performed for the safety population. Safety evaluations will be based on the incidence, severity, relatedness, and type of adverse events, as well as on clinically significant changes in the subject’s physical examination, vital signs, and clinical laboratory results. Since patients received both treatments, the AEs will be attributed to the treatment they last received.

Because there is no pre-specified safety outcome defined in terms of AEs, clinically relevant laboratory parameters, or vital signs, any formal comparisons between the treatment arms with respect to specific safety parameters will be post-hoc.

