10.2 ADVERSE EVENTS

Each AE and serious adverse event (SAE) term recorded on the case report forms (CRFs) by primary system organ class (SOC) will be mapped to a preferred term using the MedDRA dictionary. The investigator will assess AE severity and relationship to the study treatment.

A treatment emergent adverse event (TEAE) is defined as any AE that occurs within the TEAE window. This window starts on the randomization date and ends 7 days after the last dosing date for non-serious AEs and 30 days after the last dosing for SAEs. All AEs that are considered by the Investigator as treatment related will be treated as TEAEs. Only TEAEs will be summarized in tables (unless otherwise stated AEs in tables are TEAEs). However, all AEs recorded will be listed. For the purpose of calculating treatment emergence and inclusion in summary tables, incomplete onset dates will be imputed as detailed in [Appendix B](#).

AEs will be summarized by the number and percent of subjects in each primary SOC and preferred term. Patients will be counted only once for each primary SOC and each preferred term. Summary tables of AEs by primary SOC, preferred term and severity will be provided. If a subject has more than one AE coded to the same preferred term, the subject will be counted only once for that preferred term by using the event with the highest severity. Similarly, if a subject has more than one AE within a primary SOC category, the subject will be counted only once in that SOC category by using the event with the highest severity. AEs by primary SOC, preferred term and relationship to study drug will be provided as well. If a subject has more than one AE coded to the same preferred term, the subject will be counted only once for that preferred term by using the most related event. Similarly, if a subject has more than one AE within a primary SOC category, the subject will be counted only once in that primary SOC category by using the most related event. In addition, SAEs by primary SOC and preferred term will be provided. Deaths and SAEs will be summarized similarly to AEs. All adverse event tables will also include the total number of events, counting multiple events per patient.

In the AE summary, preferred terms within each SOC will appear in alphabetical order.

Frequencies for deaths and hospitalizations will also be summarized by treatment group and overall.

Other safety analyses will be performed as appropriate

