10.4 PHYSICAL EXAM

Number and percent of subjects with abnormal physical exam findings at Screening will be summarized by body system, sequence and overall. Physical Exam data for each subject will also be presented in a listing.

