14.0 APPENDICES

14.1 APPENDIX A - LIST OF TABLES, LISTINGS, AND FIGURES

List of Tables, Figures, and Listings will be documented separately.

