On Day 1 (Visit 2) eligible subjects will undergo baseline assessments and administration of the first dose of study drug in clinic. Subsequent study visits will occur on Days 15, 22, 36, and 42 (Visits 3-6). Study procedures and assessments will be performed during study visits as outlined in the Schedule of Assessments.

Study Design Schematic

PLANNED NUMBER OF SUBJECTS

Approximately 20 subjects will be enrolled in this study.

STUDY CENTERS

Up to 10 study sites in the United States and Australia.

STUDY ENTRY CRITERIA

Inclusion criteria:

A subject will be eligible for entry into the study if all of the following inclusion criteria are met:

1. Is male or female between 18 and 70 years of age, inclusive.
2. A primary diagnosis of narcolepsy with cataplexy that meets International Classification of Sleep Disorders, Third Edition (ICSD-3) criteria determined, in part, by an overnight PSG and next-day MSLT with 2 or more sleep-onset rapid eye movement (REM) periods (SOREMPs) with mean sleep latency in the pathological range (i.e. < 8 minutes). Documentation of narcolepsy with cataplexy by PSG and MSLT within 10 years of Screening is acceptable for confirmation of diagnosis.
3. Current continuing presence of EDS as defined by subject report for the last 3 months and an Epworth Sleepiness Scale (ESS) > 10 at Screening and Baseline.
4. Documented minimum of 7 cataplexy attacks per week (or 14 across two weeks) as recorded in the subject's daily diary during the Screening period.
5. If female and of childbearing potential, is nonlactating and nonpregnant (has negative pregnancy test results at Screening and Baseline).
6. If female, is either not of childbearing potential (defined as postmenopausal for at least 1 year or surgically sterile [bilateral tubal ligation, bilateral oophorectomy, or hysterectomy]) or practicing one or more of the following medically acceptable methods of birth control:

- Hormonal methods such as oral, implantable, injectable, vaginal ring, or transdermal contraceptives for a minimum of 1 full cycle (based on the subject's usual menstrual cycle period) before study drug administration.
 - Total abstinence from sexual intercourse since the last menses before study drug administration, abstinence is acceptable when it is in line with the subject's preferred and usual lifestyle.
 - Intrauterine device.
 - Vasectomized partner.
 - Double-barrier method (condoms, sponge, or diaphragm with spermicidal jellies or cream).

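### The SAP's default interval for proportions (uncorrected normal approximation) is unsuitable for about 20 subjects

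*SAP*

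**What the plan says.** SAP 6.0 (General Conventions) sets two rules for intervals. The general one is conditional: "Unless otherwise stated, confidence intervals, when presented, will be constructed at the two-sided 95% level". The specific one is that, for binomial variables, "the 95% confidence intervals will be constructed using the normal approximation without continuity correction". No exception for small counts or small denominators is visible.

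The same section has a display rule for zeros: "Presentations of categorical data will generally suppress percentages for items where the count is zero". It concerns percentages and does not mention intervals.

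The protocol synopsis gives the size: "Approximately 20 subjects will be enrolled in this study". SAP 9.5 also gives 20. SAP 4.2 plans both treatments for every subject, so a proportion by treatment has a denominator of about 20 before dropout, and one by sequence about 10.

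The visible plan for proportions is descriptive. SAP 10.2: "AEs will be summarized by the number and percent of subjects in each primary SOC and preferred term". SAP 10.4: "Number and percent of subjects with abnormal physical exam findings at Screening will be summarized by body system, sequence and overall". SAP 9.2 plans category counts for the PGI-C, with part of the method redacted there and for the NSAQ items. The one interval explicitly planned, in SAP 9.1.2, is for a mixed-model treatment difference and is not binomial. Appendix A (SAP 14.1) defers the output list: "List of Tables, Figures, and Listings will be documented separately".

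**The concern.** The Wald interval uses the observed proportion both as its centre and to estimate its own standard error. When few or nearly all subjects have the event, that standard error is too small, and at 0 or n events it is zero. With about 20 subjects such counts are to be expected for individual adverse events.

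A reader shown 0/20 with limits of 0% to 0% is told that the rate is known to be zero. A reader shown 1/20 with -4.6% to 14.6% sees an impossible lower limit and, less obviously, an upper limit well below what the data allow. SAP 3.0 commits the study report to the approved plan, so any proportion given an interval in the tables or in later safety work would take this default.

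**Working it through.** **Inputs.** Method and level: SAP 6.0 (two-sided 95%, z = 1.96). Size: n = 20 (SAP 9.5; protocol synopsis). True rates p: not given in the documents, so assumed and varied. The plan has no rate or coverage figure of its own to reproduce beyond the nominal 95%.

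**Formulas.** Wald limits for x events: x/n ± 1.96·√[(x/n)(1 − x/n)/n]. Exact coverage at rate p: the sum of Binomial(n, p) probabilities over every x whose interval contains p.

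**Limits at n = 20.** For x = 1: 0.05 ± 1.96·√(0.05·0.95/20) = 0.05 ± 0.0955, that is -4.6% to 14.6%.

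| Count | Wald | Wilson | Clopper-Pearson |
|---|---|---|---|
| 0/20 | 0.0 to 0.0% | 0.0 to 16.1% | 0.0 to 16.8% |
| 1/20 | -4.6 to 14.6% | 0.9 to 23.6% | 0.1 to 24.9% |
| 2/20 | -3.1 to 23.1% | 2.8 to 30.1% | 1.2 to 31.7% |
| 3/20 | -0.6 to 30.6% | 5.2 to 36.0% | 3.2 to 37.9% |
| 10/20 | 28.1 to 71.9% | 29.9 to 70.1% | 27.2 to 72.8% |
| 17/20 | 69.4 to 100.6% | 64.0 to 94.8% | 62.1 to 96.8% |
| 18/20 | 76.9 to 103.1% | 69.9 to 97.2% | 68.3 to 98.8% |
| 19/20 | 85.4 to 104.6% | 76.4 to 99.1% | 75.1 to 99.9% |
| 20/20 | 100 to 100% | 83.9 to 100% | 83.2 to 100% |

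**Exact coverage at n = 20.**

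| Assumed rate | P(0/20) | Wald | Wilson | Clopper-Pearson |
|---|---|---|---|---|
| 1% | 81.8% | 18.2% | 98% | 98% |
| 5% | 35.8% | 63.9% | 92% | 98% |
| 10% | 12.2% | 87.6% | 96% | 99% |
| 15% | 3.9% | 81.9% | 98% | 98% |
| 20% | 1.2% | 92.1% | 96% | 98% |
| 30% | 0.1% | 94.7% | 98% | 98% |
| 40% | <0.1% | 92.8% | 96% | 96% |
| 50% | <0.1% | 95.9% | 96% | 96% |

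**Where the misses come from.** At 1%, 5% and 10%, Wald non-coverage is 81.8%, 36.1% and 12.4%, which is almost exactly P(0/20). At 15%, non-coverage is about 18%: 3.9 points from 0/20, 13.7 from 1/20 (its upper limit, 14.6%, falls just short of 15%) and 0.6 from 8 or more events.

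**How general it is.** On 1,000 rates from 0.05% to 99.95%, Wald coverage is below 95% at 992 (99.2%). The eight exceptions lie near 14.5%, 50% and 85.5%. Over rates of 30% to 50% coverage runs from 88.4% to 95.9%, mean 92.4%.

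**Sensitivity to n.** For n = 16 to 22 and n = 24, the share of rates below 95% is 93.6% to 99.6%. At a 5% rate, coverage is 60% with n = 18 and 67% with n = 22. With about 10 subjects, as in a summary by sequence, it is 40% at a 5% rate and 84% at 30%.

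**The case against.** The strongest reply is that nothing visible uses the rule. Intervals are conditional on being presented, the safety and PGI-C summaries are counts or percentages, and SAP 10.0 says "any formal comparisons between the treatment arms with respect to specific safety parameters will be post-hoc". This stands, and it is why the point is minor. It does not remove the point. The output list is a separate document, the PGI-C and NSAQ methods are partly redacted, and SAP 10.2 leaves room for further safety analyses. Whether the default is used, or overridden, in those places cannot be known from the public text.

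Second, the worst coverage figures come from 0/20, which the zero-count display rule would often hide. Given at least one event, Wald coverage is above 99% at rates of 1%, 5% and 10%. This too is correct. But it is 85% at 15% and 93% at 20% on the same condition, and the display rule does nothing for 1/20 to 3/20 or 17/20 to 20/20.

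Third, the SAP does not use the name Wald, and the Wilson interval also rests on a normal approximation. If Wilson was meant, the problem largely disappears. Wald is the ordinary reading, and the ambiguity is cured by the same edit.

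Fourth, Wilson does not hold 95% everywhere either: at n = 20 it is below 95% at about 41% of rates on the grid. Its shortfalls are much smaller, however. Between rates of 5% and 95% its minimum is 91.9%, against 64.3% for Wald. The choice between Wilson and an exact interval is a matter of preference; the choice of either over Wald is not.

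**Conclusion.** The concern holds, as a minor correction to a default rule. At the planned size the prescribed interval falls short of its nominal level at nearly every true rate: severely at low rates, and by about 2.6 points on average between 30% and 50% (95 − 92.4). It returns zero-width or impossible limits at 8 of the 21 possible counts (0 to 3 and 17 to 20 of 20). This rests on reading the sentence as the Wald interval, on assumed event rates, and on a denominator near 20. The limits themselves depend on no assumed rate. The primary analysis is unaffected, and SAP 9.4 treats everything beyond the primary endpoint as hypothesis-generating, so no main conclusion of the trial turns on it.

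**What to change.** Replace the binomial sentence in SAP 6.0 with one that names the method, for example:

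> Two-sided 95% intervals for proportions, wherever shown, will be Wilson score intervals.

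Clopper-Pearson would also repair the rule and suits a sponsor who wants at least 95% coverage at every rate. Wilson is suggested because its coverage averages about 95% with shorter intervals.

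The cost is one sentence and one software option. Compared with Wald, Wilson is wider at very low or very high counts and 0.5 to 3.7 points narrower from 3/20 to 17/20. Its weak spots should be accepted knowingly. Coverage dips to about 89% at isolated rates between 1% and 20% and to 84.3% at the worst point of the full grid. Given at least one event, it is 88% at a 5% rate. Clopper-Pearson avoids these dips but is wider: at 10/20 its width is 45.6 points against 40.1 for Wilson.

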6.1 DEFINITION OF BASELINE

Unless otherwise stated, the last observed measurement prior to randomization will be considered the baseline measurement.

6.2 SOFTWARE

6.3 CHANGES TO PLANNED ANALYSES

Draft versions of the SAP will be numbered sequentially as Version 0.0i. The final approved version will be numbered as Version 1.00. Revisions after the “Final” version will be numbered as Version 1.0x. The Clinical Study Report will document any changes made after the final version approved before unblinding.

7.0 DESCRIPTION OF THE STUDY POPULATIONS

All tables, figures, and listings must include a population descriptor (e.g., mITT, Per Protocol or Safety) in the title.

7.1 DISPOSITION

Subject disposition summaries will be presented by treatment sequence and will include the number of subjects randomized, the number and percentage of randomized subjects in the safety, ITT, and per protocol (if applicable) populations, as well as the number and percentage of subjects who complete the study. The summaries will also include the reasons for early discontinuation from the study.

Disposition summaries will be presented for safety, mITT, and per protocol populations (if applicable) separately.

7.2 DEMOGRAPHIC AND BASELINE CHARACTERISTICS

A summary of demographics and baseline characteristics will be presented by treatment arm and overall for the mITT and safety populations. The demographic characteristics will consist of age, sex, ethnicity, region (US and ex-US), and race using descriptive statistics.

Demographic data including age, race, ethnicity, region, and gender, as well as baseline clinical characteristics will be summarized. Age will be calculated based on the following conditional algorithm:

- Has the patient had his/her birthday this year?
 - Yes, then AGE = (year of informed consent) – (year of birth).
 - No, then AGE = (year of informed consent) – (year of birth) – 1.

Clinical baseline characteristics summarized will include Narcolepsy Disease Related History.

